STUDY OUTLINE

TITLE: Evaluation of Vitamin D With And Without Hormonal Contraception on Sexual Function in Women With Polycystic Ovary Syndrome

INVESTIGATORS: [name], MMM; [name]; [name], [name]; [name]

NCT02865187

SUMMARY:

Polycystic ovary syndrome (PCOS) is the most common endocrine disorder among reproductive age women with a prevalence as high as 15%. The clinical symptoms of PCOS including menstrual dysfunction, infertility, hirsutism, alopecia, acne, and the possible increased risk of diabetes and cardiovascular disease have been reported to be significant contributors to psychological morbidity and impact health-related quality of life. For women with PCOS, the changes in physical appearance and the associated mood disorders appear to be deleterious for sexual function.

Vitamin D deficiency (<20 ng/ml serum concentration of 25[OH]D), which affects from 67% to 85% of women,⁴ is closely linked to symptoms of PCOS. The main physiologic role of vitamin D is to regulate calcium and phosphorus homeostasis and to promote bone health. Although there has been an increase in awareness of the importance of sexual dysfunction and QoL in women with PCOS, few studies have evaluated the outcomes of treatment for PCOS upon sexual and subjective health status of women.

The goals of this study are:

1. To evaluate the prevalence of sexual dysfunction (SDy) in women with Polycystic Ovarian Syndrome (PCOS)

2. To determine the effects of Vitamin D therapy, with and without hormonal contraceptives, on SDy in women with PCOS in the absence of depression.

METHODS:

The study will enroll 60 women diagnosed with PCOS and reporting SDy at the Wright State Physicians (WSP) OB-GYN Practice and the WSP Family Medicine Practice.

All participants will take vitamin D 600IU/day and will choose between hormonal and non-hormonal contraceptive methods (target of 30 participants in each group). Participants will complete three study visits (Initial, Month 3, and Month 6). Vitamin D levels will be drawn at the beginning of the study and again at 3 and 6 months after initiation of vitamin D therapy. Each participant will be asked to complete the Female Sexual Function Index (FSFI) and the Beck Depression Inventory (BDI) prior to initiation of treatment and again at 6 months.

TITLE: Evaluation of Vitamin D With And Without Hormonal Contraception on Sexual Function in Women With Polycystic Ovary Syndrome

INVESTIGATORS: [name], MMM; [name]; [name], [name]; [name]

BACKGROUND:

Polycystic ovary syndrome (PCOS) is the most common endocrine disorder among reproductive age women with a prevalence as high as 15% using Rotterdam diagnostic criteria.¹ PCOS is a heterogeneous clinical disorder characterized primarily by chronic anovulation and hyperandrogenism.² A number of other metabolic and health complications are associated with PCOS including obesity, insulin resistance, dyslipidemia, type 2 diabetes, cardiovascular disease, and endometrial cancer.³

The clinical symptoms of PCOS including menstrual dysfunction, infertility, hirsutism, alopecia, acne, and the possible increased risk of diabetes and cardiovascular disease have been reported to be significant contributors to psychological morbidity and impact health-related quality of life (HRQoL)^{4,5} including depression and anxiety,^{6,7} suicide attempts,⁸ body dissatisfaction,⁹ eating disorders,¹⁰ lower overall health-related quality of life¹¹ and diminished sexual satisfaction.^{12,13}

For women with PCOS, the changes in physical appearance and the associated mood disorders appear to be deleterious for sexual function.⁶ Previous research in this area is scant, and what has been done reveals a large number of women with PCOS (60%) reporting sexual dysfunction and that the domains of desire and arousal are most commonly affected (in 98% - 99% of cases). Using the Changes in Sexual Functioning Questionnaire (CSFQ), others have reported that women with PCOS were similar to control women in the number of sexual thoughts and fantasies and in the frequency of sexual intercourse, but differed significantly with lower orgasm/completion scores than control women.¹³ The existing research is limited by the study populations used, which have consisted of infertile women with PCOS who have a high prevalence of sexual dysfunction that may be more related to infertility and not an underlying sexual dysfunction, and by the possible impact of depression and psychotropic medications on sexual dysfunction.

Vitamin D deficiency (<20 ng/ml serum concentration of 25[OH]D), which affects from 67% to 85% of women,⁴ is closely linked to symptoms of PCOS. Observational studies have shown that lower 25[OH]D levels are associated with insulin resistance, ovulatory and menstrual irregularities, lower pregnancy success, hirsutism, hyperandrogenism, obesity, and elevated cardiovascular disease risk factors¹⁴ as well as decreased HRQoL and depression in select

populations.¹⁵ Nonetheless, there is limited research exploring the implications of vitamin D status and replacement on HRQoL issues including SDy.

The main physiologic role of vitamin D is to regulate calcium and phosphorus homeostasis and to promote bone health. However, accumulating evidence suggests that vitamin D deficiency may also be an important factor for many other diseases. Several mechanisms of action have been proposed to explain the association between vitamin D and depression.

The role of calcitriol or 1,25 dihydroxy cholecalciferol, the bioactive form of vitamin D, in brain tissue has been confirmed by the presence of vitamin D receptors (VDRs) and hydroxylases in various brain regions. One area where VDRs and hydroxylases have been found in the amygdala, the center of the limbic system, where behavior and emotions are regulated.¹⁶ In addition, Vitamin D is involved in numerous brain processes including neuroimmunomodulation, regulation of neurotrophic factors, neuroprotection, neuroplasticity and brain development,¹⁶ making it biologically plausible that vitamin D might be associated with HRQoL and SDy.

Although there has been an increase in awareness of the importance of sexual dysfunction and QoL in women with PCOS, few studies have evaluated the outcomes of treatment for PCOS upon sexual and subjective health status of women. Therapy has been directed at treating the physical symptoms produced by chronic anovulation, hyperandrogenism and metabolic disturbances associated with insulin resistance of PCOS. Treatment for PCOS has included oral hypoglycemic agents, laparoscopic wedge resection, and cosmetic procedures, such as laser hair removal, but the mainstay remains combined hormonal contraception.

The specific contribution of estrogens and progestogens in oral contraceptives is not fully understood, particularly the latter as it has variable potency and androgenicity. In general, the most commonly used progestins are the 19-testosterone derivatives. Newer oral contraceptives, such as drospirenone, norgestimate, and desogestrel, contain less androgenic progestins. Drospirenone is a 17-alpha spironolactone derivative progestin with antiandrogenic and antiminerlocorticoid activity. Studies have shown various benefits of combined hormonal contraceptives for PCOS patients who are not pursuing fertility, e.g., management of endocrine and metabolic profiles, androgen levels, and endometrial cancer.⁵

Vitamin D supplementation has also been reported to improve glucose metabolism and menstrual frequency in PCOS women¹⁷ and since Vitamin D deficiency is closely linked to PCOS and depression, its supplementation has been suggested to possibly play an important part in the treatment of PCOS and HRQoL and perhaps SDy.¹⁸

As such, the goal of this study is to evaluate the prevalence of sexual dysfunction and assess the impact of treatment using oral contraceptives with Vitamin D on SDy in absence of depression. We anticipate this may provide a new treatment strategy in SDy issues for women with PCOS.

OBJECTIVES:

1. To evaluate the prevalence of sexual dysfunction (SDy) in women with Polycystic Ovarian Syndrome (PCOS)
2. To determine the effects of Vitamin D therapy, with and without hormonal contraceptives, on SDy in women with PCOS in the absence of depression.

METHODS:

The study will enroll 60 women diagnosed with PCOS and reporting SDy at the Wright State Physicians (WSP) OB-GYN Practice and the WSP Family Medicine Practice.

All participants will take vitamin D 600IU/day (as recommended by the National Institutes of Health's Office of Dietary Supplements) and will choose between hormonal and non-hormonal contraceptive methods (target of 30 participants in each group). Participants will complete three study visits (Initial, Month 3, and Month 6). Vitamin D levels will be drawn at the beginning of the study and again at 3 and 6 months after initiation of vitamin D therapy. Each participant will be asked to complete the Female Sexual Function Index (FSFI) and the Beck Depression Inventory (BDI) prior to initiation of treatment and again at 6 months.

Inclusion / Exclusion Criteria:

Women will be included in the study if they meet the following inclusion criteria and none of the exclusion criteria listed below:

Inclusion criteria:

- 1) Are reproductive age from 18-40 years old;
- 2) Have a diagnosis of PCOS using the revised 2003 Rotterdam European Society for Human Reproduction (ESHRE) criteria in which the following are present:
 - a) Oligomenorrhea (cycles lasting longer than 35 days) or amenorrhea (fewer than 3 cycles in the past 6 months);
 - b) Either clinical signs of hyperandrogenism (hirsutism with a Ferriman-Gallwey score of more than 7 or obvious acne or pronounced alopecia) or an elevated total testosterone (>2.0 nmol/L); **or**

- c) Poylecystic appearing ovaries.
- 3) Report SDy according to the FSFI; and
- 4) Have no evidence of severe depression as measured by the BDI >30.

Exclusion criteria:

- 1) Patients with chronic medical illness, such as, diabetes mellitus, hypertension and previous venous embolism
- 2) Are taking any prescription medications for at least 3 months prior to entering the study, with the exception of allergy and occasional pain medications
- 3) Have other etiologies of anovulation and hyperandrogenism (e.g., Cushing's, thyroid dysfunction, elevated prolactin levels, signs of congenital adrenal hyperplasia)
- 4) Have any contraindications to hormonal contraception

Recruitment:

Participants will be recruited from the Wright State Physicians Obstetrics and Gynecology and Family Medicine practice offices. The opportunity to be involved in this research project will be approached at their clinic visit with the physician if the patient meets selection criteria. A consent form will be given and the study will be discussed.

In addition, print advertisements will be placed in the local Reach magazine to recruit patients in the Dayton area.

Stipends:

Participants will receive a stipend in the form of a MasterCard gift card for their time and travel. After each completed study visit the participant will be provided with a gift card -in the amounts as follows: \$50 at Visit 1 and Visit 3, and \$35 at Visit 2 for a maximum per patient compensation of \$135.

HUMAN SUBJECTS PROTECTION:

The PI is responsible for protection of human subjects. This protocol will be reviewed by the WSU Institutional Review Board. Only subjects who meet study eligibility criteria will be enrolled. All eligible participants will have the study explained to them. The informed consent process will be conducted appropriately and the informed consent will be obtained prior to proceeding with any study procedures.

The primary physician or the Principal Investigator and research associates will be the individuals obtaining informed consent from patients. They will be uniform in their explanations of the nature of the study to all patients who fit the selection criteria. Those patients interested in

participating will be given time to read over the informed consent. The patients will be asked either in the clinic to be involved in the study. After the informed consent is reviewed by the patient any remaining questions will be answered.

Adverse events will be reviewed and evaluated by the PI throughout the study. In the event that any additional diagnoses are obtained during this study, the primary physician for the patient will be notified. It will be their responsibility to notify the patient of these diagnoses and any changes to management that may result.

Subjects' confidentiality will be protected. Participants will be assigned a unique identification (ID) number for the study that will be used on data collection forms rather than subjects' names. Only the minimum data necessary to conduct the study and meet the objectives will be collected. Data will be stored in a secure database (REDCap¹⁹) that uses a unique username and password for each team member. Data will be de-identified prior to analysis.

SIGNIFICANCE OF THE STUDY IN RELATION TO HUMAN HEALTH (BENEFITS):

PCOS is the most common reproductive endocrine disorder that has a number of health quality of life issues. The benefit of this study will be to identify SDy which is often overlooked and may potentially be helped with Vit D and/or birth control.

POTENTIAL HAZARDS (RISKS):

The study questionnaires may evoke stressful feelings taking a psychosocial questionnaire. In addition, there are rare potential risks related to OCPs including deep venous thrombosis, and stroke.

Serious side effects of vitamin D include allergic reactions, swelling of the face, throat, and tongue, dizziness, irregular or racing heart beat, dry mouth, headache, vomiting, weakness and lack of energy, and fatigue

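### Objective 2 claims an effect of vitamin D, but the only planned FSFI analysis is an uncontrolled before-after test in women who all take it

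*Protocol*

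**What the plan says.** The second objective in the Protocol (Objectives) reads "To determine the effects of Vitamin D therapy, with and without hormonal contraceptives, on SDy in women with PCOS".

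Under Methods, "All participants will take vitamin D 600IU/day", and participants "will choose between hormonal and non-hormonal contraceptive methods (target of 30 participants in each group". The two groups therefore differ in the contraceptive method each woman chooses, not in vitamin D. Neither document describes a group without vitamin D, a placebo, randomisation, blinding or an untreated run-in.

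The sample is set by one sentence: "The study will enroll 60 women diagnosed with PCOS and reporting SDy". Sexual dysfunction at entry is defined by the FSFI (Inclusion criteria, item 3). The FSFI is completed once before treatment and once at 6 months.

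The SAP is one short paragraph. It compares baseline with 6 months for the FSFI (total and subscales) and for vitamin D level, using a paired t-test. It plans no comparison of the contraceptive groups and does not say whether the paired test is run on all women together or by group.

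**The concern.** An objective that sets out to determine the effect of a treatment needs an estimate of what would have happened without it. Nothing in this design supplies one. A paired test asks whether FSFI scores moved over 6 months; it cannot say why.

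Scores have several reasons to move even if vitamin D does nothing. Time passes. Participants rate themselves after starting a treatment, with no placebo or blinding described. The women were selected for poor scores on the same scale that measures the outcome, so their second score is expected to be higher on average. About half of them are also meant to use hormonal contraception during the same 6 months.

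What is at stake is the conclusion. Read against Objective 2 as worded, a significant paired test would look like the answer to the vitamin D question, although it would not be one.

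**Working it through.** **The plan's own figure.** 30 + 30 = 60, which agrees with the stated enrolment. Nothing further can be reproduced, because the documents give no alpha, power, effect size, standard deviation or dropout.

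**What the planned test estimates.** Let V be the vitamin D effect, T time and expectation, R regression to the mean, H the hormonal contraceptive effect and S any difference due to self-selection. With additive effects, the mean FSFI changes are:

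- non-hormonal group: V + T + R
- hormonal group: V + T + R + H + S
- both pooled, 30 + 30: V + T + R + (H + S)/2

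V is present in each line but never alone.

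**How large R could be.** This is an illustration. From the documents: n = 60, entry on the FSFI, and the 60% of women with PCOS reporting sexual dysfunction (Protocol, Background). Assumed, not in the documents: normal scores, enrolment of the lowest 60% of the distribution, the screening score used as baseline, two-sided alpha 0.05, and a test-retest correlation ρ between 0.5 and 0.9.

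The 60% cut-point is 0.253 SD, and the mean baseline score of those enrolled is −φ(0.253)/0.6 = −0.644 SD. With V = T = H = S = 0, the expected rise is R = (1 − ρ) × 0.644 SD. In 20,000 simulated trials per setting, the paired t-test was significant as follows:

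| ρ | R (SD) | significant, n = 60 | significant, 30 non-hormonal women |
|---|---|---|---|
| 0.9 | 0.06 | 20% | 12% |
| 0.8 | 0.13 | 36% | 20% |
| 0.7 | 0.19 | 51% | 27% |
| 0.6 | 0.26 | 65% | 37% |
| 0.5 | 0.32 | 76% | 45% |

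Hand check at ρ = 0.7. The baseline variance among those enrolled is 1 − 0.253 × 0.644 − 0.644² = 0.422. The variance of the change is 0.3² × 0.422 + (1 − 0.7²) = 0.548, so its SD is 0.740 and the standard error is 0.740/√60 = 0.0956. R divided by this is 0.193/0.0956 = 2.02. The critical value is about 2.00, so the test rejects in about half of trials, as simulated.

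**Effect of pooling.** With V = 0, H = 0.3 SD (assumed) and ρ = 0.7, the pooled change is 0.193 + 0.3/2 = 0.343 SD, and the pooled test was significant in 94% of simulated trials.

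**Would a group contrast help?** It is not planned, but it is the obvious alternative. (V + T + R + H + S) − (V + T + R) = H + S, so V drops out. In simulation with H = 0.3 SD, S = 0 and ρ = 0.7:

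| V (SD) | change, hormonal | change, non-hormonal | difference |
|---|---|---|---|
| 0 | 0.50 | 0.19 | 0.30 |
| 0.3 | 0.79 | 0.49 | 0.30 |
| 0.5 | 0.99 | 0.69 | 0.30 |
| 0.8 | 1.30 | 0.99 | 0.30 |

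Adding a vitamin D-by-contraceptive interaction of 0.2 SD moves the difference to 0.50 SD, which is H plus the interaction. V is still not estimated.

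**The case against.** **Cancellation is not how the planned analysis fails.** A reader might infer that the trial's analysis subtracts the vitamin D effect away. It does not: the SAP plans no group comparison, and in the paired test V is confounded rather than cancelled. This stands, so the cancellation argument is secondary. It is also exact only under additivity and if time, expectation and regression act alike in both groups.

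**The rest of the protocol is more careful than Objective 2.** A reader might infer that the whole protocol promises a vitamin D effect. The title speaks only of evaluation. The benefits section says that sexual dysfunction "may potentially be helped with Vit D and/or birth control", which is hedged and not specific to vitamin D. The goal statement, "We anticipate this may provide a new treatment strategy in SDy issues for women with PCOS", is also hedged and follows a sentence about oral contraceptives together with vitamin D. This stands: only Objective 2 makes the claim.

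**The data are not without value.** The study can describe the change in FSFI and in vitamin D level. A flat FSFI score in the non-hormonal group, or no rise in vitamin D level, would count against a vitamin D effect. This also stands. The design can disappoint the hypothesis; it cannot attribute an improvement to vitamin D. Measuring vitamin D levels does not change that, since the SAP plans no analysis linking them to the FSFI, and such a link would be observational.

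**Some premises are inferred.** Open-label treatment is inferred from the absence of any described placebo or blinding. How results will be reported is not stated in either document, so misreporting should not be presumed.

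**Conclusion.** Wrong as written. Objective 2 asks for an effect that neither the planned paired test nor any contrast available in the design can isolate. This follows from the structure alone: the same vitamin D for everyone, no comparator without it, and a single before-after test.

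The size of the possible error is only illustrated. Regression to the mean by itself could make the test on 60 women significant in about 20% to 76% of trials with no treatment effect, against a nominal 5%. Those percentages depend on normal scores, enrolment of the lowest 60%, use of the screening score as baseline, and a correlation from 0.9 down to 0.5. They are not this trial's error rate; a separate baseline measurement after screening, for example, could reduce them. The failure to identify a vitamin D effect does not depend on them.

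**What to change.** **Protocol.** Reword Objective 2 along these lines: *to describe the 6-month change in FSFI among women taking vitamin D, by chosen contraceptive group*. The title and benefit statement need no change.

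**SAP.**
- Report the paired changes separately by contraceptive group.
- State that they are uncontrolled before-after changes, open to time, expectation and regression to the mean, and will not be reported as effects of vitamin D.
- State that any between-group difference, if reported, concerns self-chosen contraception on top of vitamin D.

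**Cost.** Wording only, with no new arm, participants or visits. The downside is a less favourable stated claim. Keeping the causal objective would instead require a concurrent comparator without vitamin D, which is a different study.

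### No planned record of contraceptive use at Months 3 and 6, and no rule for classifying women who change method, leaves the with/without reading of Objective 2 uninterpretable for switchers

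*Protocol*

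**What the plan says.** The second objective in the protocol is "To determine the effects of Vitamin D therapy, with and without hormonal contraceptives, on SDy in women with PCOS in the absence of depression". Hormonal contraception is thus one half of the exposure the trial sets out to study.

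The METHODS section gives the size and the grouping: "The study will enroll 60 women diagnosed with PCOS and reporting SDy", all on vitamin D, who "will choose between hormonal and non-hormonal contraceptive methods (target of 30 participants in each group". Groups are formed by the woman's own choice.

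The schedule is in the same section. "Participants will complete three study visits (Initial, Month 3, and Month 6". For the laboratory measure the text reads: "Vitamin D levels will be drawn at the beginning of the study and again at 3 and 6 months after initiation of vitamin D therapy". The FSFI and BDI are completed "prior to initiation of treatment and again at 6 months". No contraceptive product, start date, continued use, stop or switch is listed for any visit. There is no rule for the group of a woman who changes method.

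Two further places bear on this. Human Subjects Protection states: "Only the minimum data necessary to conduct the study and meet the objectives will be collected". It also provides for review of adverse events throughout the study. The second exclusion criterion applies to women who "Are taking any prescription medications for at least 3 months prior to entering the study, with the exception of allergy and occasional pain medications".

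The SAP is one paragraph. It plans paired t-tests of baseline against 6 months for FSFI total and subscale scores and for vitamin D levels. It does not mention contraceptive group.

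**The concern.** The only FSFI after baseline is at Month 6. To read it as a result with or without hormonal contraception, the analyst must know what the woman was using then and in the months before. The plan as written does not produce that information. A woman who chose a hormonal method and stopped in month 2, and a woman who chose a non-hormonal method and started a pill in month 3, could not be told apart from women who kept to their choice.

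The two halves of the objective are served unequally. Serum vitamin D is drawn at Months 3 and 6, which gives at least indirect evidence of exposure, although the protocol does not call it an adherence check. The contraceptive half has nothing comparable.

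The second exclusion criterion may sharpen the point. Read literally, it would cover prescribed contraceptives, so the hormonal group would be mostly new starters, and whether they continue to Month 6 would matter more.

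At stake is what the Month 6 FSFI can be said to show. If women stop a hormonal method because of mood or sexual effects, their score off the method would be credited to hormonal contraception. Dates and reasons not recorded during the trial are hard to recover afterwards.

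**Working it through.** **Inputs from the documents.** 60 women, target 30 per group, group by choice, FSFI at baseline and Month 6. The documents give no alpha, power, effect size, SD or switching rate, so there is no figure of the plan's own to reproduce.

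**Step 1: which analyses are exposed.**
- The SAP's paired test, pooled over all women, does not use contraceptive group, so no woman is misclassified in it.
- Objective 2 cannot be answered from that pooled test. It needs either a between-group comparison of FSFI change or, at the least, the paired tests run separately by group. Both need a definition of group, and both can mix women on and off method.

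**Step 2: switching unrelated to outcome.** Let a be the share of hormonal choosers off method at Month 6 and b the share of non-hormonal choosers on one. Let D be the true effect, and suppose switchers take on the full effect of the regimen they move to.

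- Hormonal choosers: (1 − a)D. Non-hormonal choosers: bD.
- Observed difference by choice: (1 − a − b)D.

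As an illustration only, take a true difference of 0.75 SD of the change score, 30 per group, and a two-sample t-test at two-sided 0.05 (noncentral t). The rates, the effect and the test are all assumptions.

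| a / b (assumed) | Share retained | Difference (SD) | Power |
|---|---|---|---|
| 0% / 0% | 1.00 | 0.75 | 0.815 |
| 10% / 5% | 0.85 | 0.75 × 0.85 = 0.6375 | 0.680 |
| 20% / 10% | 0.70 | 0.75 × 0.70 = 0.525 | 0.516 |
| 30% / 10% | 0.60 | 0.75 × 0.60 = 0.45 | 0.403 |
| 40% / 20% | 0.40 | 0.75 × 0.40 = 0.30 | 0.208 |

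With no switching there is no loss.

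**Step 3: switching related to outcome.** Let a share s of hormonal choosers stop, with no lasting effect at Month 6, and let nobody start. Write e₁ for the effect in women who continue and e₂ for the effect that the stoppers would have had on the method.

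- Average effect of the method: (1 − s)e₁ + s·e₂.
- Observed by choice: (1 − s)e₁.
- Observed minus average: −s·e₂.

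With s = 0.20 and e₂ = −0.5 SD (women harmed, who stop), the error is +0.10 SD and harm is hidden. With e₂ = +0.5 SD it is −0.10 SD. The direction depends on why women stop, which the plan does not record.

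**Step 4: why an on-method analysis cannot be the main one.** Suppose stoppers differ in FSFI change by g whatever the method, the same mix of such women is in both groups, and the true effect is e. Hormonal stayers average e; non-hormonal choosers average s·g. The on-method contrast is e − s·g. With e = 0, s = 0.20 and g = −1 or +1 SD, it shows +0.20 or −0.20 SD where there is no effect. The comparison by initial choice gives (1 − s)e = 0 under the same assumptions.

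**The case against.** The strongest reply is that the documents are brief and their silence proves little. A reader might infer that the group is locked at entry and that use is never asked about again. The documents say neither. Visits exist at Months 3 and 6 where use could be asked, and adverse events are reviewed throughout. The statement on minimum data allows whatever the objectives need, so it cannot be cited as proof that use goes unrecorded. This stands: the defect is an unspecified record and an undefined classification. Adverse-event review does not close the gap, since it is not a record of use and is unlikely to show a non-hormonal chooser starting a hormonal method.

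A reader might also infer that a planned contrast is diluted toward no difference. That is not supported either. The SAP names no with/without comparison, so no planned test can be diluted, and the absence of that comparison is the more basic gap. Dilution toward zero also requires switching unrelated to outcome, which cannot be assumed when mood or sexual effects may prompt a change. Adding a between-group test to the SAP would not, however, supply the missing data on use.

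Finally, women choose their own method, so confounding by choice would remain even if nobody switched. That is correct, and recording use does not cure it.

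**Conclusion.** The point holds in a limited form. Contraceptive use after the initial choice is not among the planned measurements, and neither document says how a woman who changes method is classified, although Objective 2 depends on that exposure. Any with/without reading of the Month 6 FSFI, including paired tests run by group, could combine women on and off the method they are counted under.

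The direction of bias is unknown, and its size cannot be computed from the documents. The factor 1 − a − b applies only if switching is unrelated to outcome and switchers take on the full effect of their new regimen. The power figures are illustrations for a test the SAP does not plan and should not be quoted as properties of this trial. Because the recommended main grouping is still initial choice, the gain from the change is interpretability and not power. It is a cheap improvement that should be made.

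**What to change.** **Protocol, METHODS.** At the existing Month 3 and Month 6 visits, record the contraceptive method in use and the date and reason of any stop or switch.

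**SAP.**
- Add the with/without comparison of FSFI change from baseline to Month 6, which is currently absent, and define its groups by initial choice.
- Report the number of women who crossed over in each direction.
- Add a supportive analysis of FSFI change in women who stayed on their chosen method type through Month 6.

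**Cost.** A few data items at visits already scheduled, and one supportive analysis. The on-method subset will be smaller and self-selected, so it supports the initial-choice result and does not replace it. None of this removes confounding by choice or restores power lost to switching.

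### Contraceptive group is self-chosen and the SAP has no group contrast or adjustment, so a with-versus-without difference in FSFI cannot be attributed to contraception

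*Protocol*

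**What the plan says.** Allocation is by preference. The Protocol's Methods (and its Study Outline) state that participants "will choose between hormonal and non-hormonal contraceptive methods", with a "target of 30 participants in each group". No randomisation, matching or stratification is described. All women take the same vitamin D supplement, so contraceptive method is the only thing that distinguishes the groups by design.

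Objective 2 is worded causally: "To determine the effects of Vitamin D therapy, with and without hormonal contraceptives, on SDy in women with PCOS in the absence of depression". The end of the Background likewise speaks of assessing the impact of oral contraceptives given with vitamin D.

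The Background says that in PCOS "the changes in physical appearance and the associated mood disorders appear to be deleterious for sexual function". It criticises earlier work in infertile women for a "high prevalence of sexual dysfunction that may be more related to infertility and not an underlying sexual dysfunction". It describes combined hormonal contraception as the main treatment for PCOS, and reports "benefits of combined hormonal contraceptives for PCOS patients who are not pursuing fertility".

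The study measures named in Methods are FSFI and BDI before treatment and at 6 months, and vitamin D level at baseline, 3 and 6 months. Age, menstrual pattern and hyperandrogenism are assessed for eligibility. The SAP consists of paired baseline-to-6-month t-tests on FSFI total, FSFI subscales and vitamin D. It does not mention contraceptive group, BDI or any covariate.

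**The concern.** Symptom burden, mood and fertility intention could each affect both the method a woman picks and how her sexual function develops over 6 months. If so, the two groups would differ in FSFI course even if contraception did nothing.

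The missing group test does not remove the problem. Objective 2 invites a with-versus-without reading, and a reader can get there by setting one group's paired result beside the other's. That route carries the same selection, and it is also not a test of the difference.

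At stake is whether the study can say anything about contraception under Objective 2. Timing matters too: reason for choice, fertility intention and pre-treatment symptom severity are best recorded before treatment starts, because later recall or on-treatment values are poor substitutes.

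**Working it through.** **1. Plan's own figure.** There is none to reproduce. The Protocol states "The study will enroll 60 women diagnosed with PCOS and reporting SDy" without alpha, power, effect size, SD or dropout.

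**2. Possible drivers of choice set against what is recorded.**

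| Possible driver | Basis in the Protocol | Status as data |
|---|---|---|
| Mood | Background: affects sexual function | BDI at baseline and 6 months |
| Baseline sexual function | Inclusion criterion 3 | FSFI at baseline and 6 months |
| Appearance, hyperandrogenism | Background: affects sexual function | Assessed for eligibility; retention of graded values not stated |
| Age, menstrual pattern | Eligibility only | Assessed for eligibility; retention not stated |
| Fertility intention | Background: infertility and sexual function; contraceptive benefits when not seeking fertility | Not named |
| Reason for choice, BMI, relationship status | None stated | Not named |
| Earlier hormonal use | Exclusion 2 bears on prescription medicines in the 3 months before entry | Not named |

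Eligibility removes some drivers. Exclusion 4 takes out women with contraindications to hormonal contraception, and inclusion criterion 4 is evidently meant to take out severe depression (BDI above 30).

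**3. Illustrative size of bias.** Assume that contraception has no true effect, that all 30 women per group complete, and that a two-sample t-test at two-sided 0.05 is applied to FSFI change. Let a prognostic factor differ by s SD between the groups and have correlation r with FSFI change. Then bias = r × s in SD of change, and the noncentrality is bias / √(2/30) = bias / 0.258, on 58 degrees of freedom.

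| r | s | Bias (SD) | Noncentrality | False-positive rate |
|---|---|---|---|---|
| 0.3 | 0.3 | 0.09 | 0.35 | 6.4% |
| 0.4 | 0.5 | 0.20 | 0.77 | 11.9% |
| 0.5 | 0.8 | 0.40 | 1.55 | 33.2% |

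Every r and s is an assumption; the documents give neither.

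**4. What measurement buys.** This was simulated with 30 per group, 5,000 runs, no true effect and an assumed total bias of 0.6 × 0.5 = 0.30 SD. The unadjusted test rejects in about 20% of runs. Adjusting for a covariate that carries half the bias leaves about 0.15 SD and 8%. Adjusting for one that carries all of it leaves about 0 SD and 5%. Confounding is therefore reducible to the extent that its sources are measured.

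**5. Scale of the study.** With 30 per group, 80% power in an unadjusted t-test needs a true difference of about 0.74 SD. Power is about 49% at 0.5 SD (normal approximation). A bias at the upper end of the table is not small beside effects of that order.

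**The case against.** Several counter-arguments have force.

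- **A reader might infer that none of the drivers of choice is recorded.** The documents do not support this. Mood, which the Background names, is captured by the BDI before treatment, and baseline FSFI is also held.
- **A reader might infer that confounding is beyond repair.** It is not. Adjustment for baseline FSFI and BDI is possible with data already planned, and a few further items would allow more. What cannot be adjusted for is a driver left unrecorded.
- **A reader might infer that BMI, relationship status and the rest will not be collected.** That would be an argument from silence, since no case report form is among the documents. The sentence "Only the minimum data necessary to conduct the study and meet the objectives will be collected" is a confidentiality statement and does not bar covariates that serve the objectives. The most that can be said is that there is no commitment to keep them as analysis data.
- **The link between symptoms and choice is inferred.** The Background makes it plausible but never states why women choose a method. The eligibility limits also narrow the possible imbalance.
- **The Background speaks to level, the SAP to change.** Stable differences in level cancel from change scores, so bias requires factors that predict change. This is fair, and it is why the correlations above remain assumptions.
- **The false-positive rates describe a test that the SAP does not plan.** This is also correct. They give scale and are not operating characteristics of this plan.

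None of this supports reading a with-versus-without difference as an effect of contraception. The groups are self-chosen, the objective is causal in wording, and no adjustment is stated.

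**Conclusion.** The point holds in this form: contraceptive group is self-selected, the Background names factors that could plausibly act on both the choice and sexual function, and the plan contains neither a group contrast nor an adjustment. Following it as written could not support a contraceptive effect under Objective 2.

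The size of any bias cannot be derived from the documents. The range of 0.09 to 0.40 SD, with 6% to 33% false positives, shows only what moderate imbalance could do under the stated assumptions. The change is worth making because it is cheap and because the missing information is best captured before treatment.

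**What to change.** - **SAP.** Add a with-versus-without contrast in 6-month FSFI, adjusted for baseline FSFI, baseline BDI and a very short pre-stated list of further covariates. Give a baseline table by group.
- **Visit 1 form.** Record reason for choice, fertility intention, earlier hormonal contraceptive use, BMI and relationship status. Carry age and the eligibility findings on hyperandrogenism (Ferriman-Gallwey score, acne, alopecia, testosterone), where available, into the dataset.
- **Objective 2.** Reword it so that the contraceptive contrast is an association between self-chosen groups.

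**Cost.** About half a page on the Visit 1 form and one SAP paragraph, with no new procedure. The claim becomes weaker. Some degrees of freedom are spent: with group, baseline FSFI, baseline BDI and, for example, three further covariates, the residual degrees of freedom are 60 − 7 = 53, against 58 unadjusted. Residual confounding from unmeasured drivers would remain, and the report should say so.
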